1 SYNOPSIS

African Americans have 22% higher incidence and 49% higher death rates from colorectal cancer (CRC) than any other ethnic/racial group. Similarly, lower socioeconomic status (SES) is also associated with higher CRC incidence and mortality. Both of these groups are overrepresented in Medicaid populations. Screening colonoscopy is the “gold standard” for cost-effective cancer prevention and control and several fecal tests (e.g., FIT) are reliable alternatives. However, Medicaid clients have much lower screening rates causing large “gaps in care” – contributing to higher CRC morbidity and mortality—and are major challenges for health insurance companies and clinical practices which are negatively impacted by the lower quality metrics and reduced financial benefits that result from lower screening rates. Improving CRC screening rates is therefore a strategic priority for both health care providers and insurers. The mission of Witness CARES, LLC, is to improve people’s lives by facilitating use of health care. The goal of this Phase I STTR proposal is to test the feasibility of providing specialized services (i.e., *WC Services*) to increase CRC screening for Medicaid clients and thereby improve metrics for our health insurance (YourCare and clinical practice (Mercy Comprehensive Care Center) customers. Based on prior research and experience, we will conduct a small pilot effectiveness study combining a broad range of services to educate, activate and navigate these “gaps in care” clients for a broader market (not just a single facility or patients with screening referrals) in order to test the feasibility for future commercialization. In addition, we will evaluate these clients to develop a predictive algorithm for assessing likelihood of CRC screening outcome. We propose the following specific aims: **Aim 1:** Test the feasibility of *WC Services* to achieve CRC screening for non-adherent Medicaid clients. **Milestone 1a:** Achieve colonoscopy by a minimum of 60 out of 200 ($\geq 30\%$) patients contacted. **Milestone 1b:** Achieve CRC stool screening for 70 of the 140 colonoscopy non-adherent clients. **Milestone 1c:** *WC Services* will be revised to produce a new prototype to test in a Phase II based on feasibility findings. **Aim 2:** Develop an algorithm for predicting CRC screening outcomes following intervention services. **Milestone 2a:** Develop models based on existing R01 data to predict intent and CRC screening behaviors. **Milestone 2b:** Revise this R01 model incorporating new measures collected prospectively with 80% of clients contacted (n=160) to identify variations for likelihood of stool test v. colonoscopy completion. **Milestone 3** will be the Phase I report of these findings. Successful completion of these aims are expected to show the acceptability and feasibility of *WC Services* to improve CRC screening rates for Medicaid patients and develop assessment tool(s) that enable us to evaluate this product in a randomized controlled trial in a Phase II study with a special emphasis on reducing CRC disparities in minority and lower income populations.

2 BACKGROUND

Colorectal cancer (CRC) is the second leading cause of cancer deaths in the U.S.¹ African Americans have 22% higher incidence and 49% higher death rates from CRC than any other ethnic/racial group.¹ Similarly, lower socioeconomic status (SES) is also associated with higher CRC incidence and mortality.² Both of these groups are overrepresented in Medicaid populations.³ Amongst screening options for average-risk individuals, both stool tests (e.g., fecal immunochemical-FIT or DNA-mtsDNA/Cologuard®) and colonoscopy are deemed effective;⁴ with colonoscopy being the most effective at reducing CRC incidence.^{5,6} Adherence to CRC screening guidelines is poor for African American and low SES groups,⁷ even for insured individuals. In New York State (NYS), over 80% of CRC screening non-adherent individuals are insured. Lack of screening in insured adults is a “gap in care” that poses significant challenges for insurers, including reduced quality metrics (i.e., Medicare Star and Healthcare Effectiveness Data & Information Set - HEDIS® scores) which negatively impacts financial bonus payments to these companies. Increased CRC screening is a high value product in the health care market as

well as addressing cancer disparities.

Disparities and low screening rates exist primarily because of a host of structural (e.g., access, transportation) and individual barriers (e.g., fear, negative affective associations, daily life issues) experienced by lower income and minority patients that are generally beyond the scope of clinical practices and health insurance companies to address. Approaches to address these barriers have been proven effective by our team and others for various screening services but have not been tested as a marketable commodity. These proven methods include the use of patient navigation,^{8,9} culturally appropriate education,^{10,11} and community-based participatory processes.^{12,13} However, navigation services are not reimbursable expenses for clinical providers, require specialized expertise and access to multiple ancillary services (e.g., transportation). Health insurers have experimented with monetary incentives, reminders and incentivizing health providers, but these approaches are limited and do not address the basic structural and individual barriers influencing behaviors. But if proven to reduce “gaps in care”—insurance companies *will* outsource and pay for these services (e.g., see Letters; and National Witness Project (NWP) in Facilities and Resources). Effective programs offering multi-level services to optimize screening for non-adherent clients are not readily available for insurers or clinicians to adopt or purchase. Witness CARES, LLC proposes to remedy this gap by offering a full-service resource for educating, activating and navigating clients to screening for insurance companies (e.g., YourCare, see Letter) and for primary care clinics (e.g., Mercy Comprehensive Care Center, see Letter). Moreover, although there is an extensive body of work examining decision-making predictors of successful CRC screening,^{14,15} there are not easily implementable tools for predicting compliance in real time, or to assess for which clients at-home stool testing versus colonoscopy screening is likely to be most achievable. This STTR Phase I study provides an opportunity for Witness CARES, LLC to explore the feasibility of providing these services to Medicaid clientele to satisfy the screening expectations of insurers and primary care providers (Aim 1), and the feasibility of developing a predictive tool(s) (Aim 2) for determining which screening test is most appropriate for clientele.

Specialized Interventions. Our team has developed and implemented effective, specialized interventions for over 20 years to reach, educate, activate and navigate African American and low SES clients into cancer screening.^{16,17} For example, patient navigation by lay navigators (Consultant, [name]) increased adherence to screening colonoscopy to 66.4% among urban minority patients¹⁸ at a cost of only \$29/patient screened. Our sister, not-for-profit, The National Witness Project (NWP) (See Facilities and Resources), has provided specialized services to health insurance companies in western New York (WNY) on a contractual basis (> \$600K) for over three years, screening over 3000 women with mammograms and Pap tests, and demonstrating a potential market for CRC screening navigational services. Witness CARES, LLC needs to conduct this Phase I study to determine if we can create a similar group of services and assessments specialized for increasing CRC screening based on findings about behavioral constructs impacting CRC screening behaviors from our R01 CA171935 study.^{19,20} If proven feasible in this Phase I study, this will be a novel set of services to offer health insurance companies and their clinical practices, with the added innovative technology of an algorithm for predicting screening preferences for this Medicaid population. This would be an important service for over 835,000 African American men and women, and 104,752 additional Medicaid clients between the ages of 50 and 79 who have not had a timely colonoscopy and/or other fecal testing for CRC screening in New York State.^{1,21,22} Achieving the aims of this STTR feasibility study, *Witness CARES, LLC has a significant opportunity to develop a feasible prototype for WC Services to improve CRC screening by Medicaid clients and initiate the development of predictive measures to determine the most acceptable CRC screening test.*

3 RATIONALE

The National Witness Project (NWP), has provided specialized services to health insurance companies in western New York (WNY) on a contractual basis for over three years, screening over 3000 women with mammograms and Pap tests, and demonstrating a potential market for CRC screening navigational services. Witness CARES, LLC needs to conduct this Phase I study to determine if we can create a similar group of services and assessments specialized for increasing CRC screening based on findings about behavioral constructs impacting CRC screening behaviors from our R01 CA171935 study.^{19,20} If proven feasible in this Phase I study, this will be a novel set of services to offer health insurance companies and their clinical practices, with the added innovative technology of an algorithm for predicting screening preferences for this Medicaid population. This would be an important service for over 835,000 African American men and women, and 104,752 additional Medicaid clients between the ages of 50 and 79 who have not had a timely colonoscopy and/or other fecal testing for CRC screening in New York State.^{1,21,22} Achieving the aims of this STTR feasibility study, *Witness CARES, LLC has a significant opportunity to develop a feasible prototype for WC Services to improve CRC screening by*

4 OBJECTIVES

The goal of this Phase I application is to prove the feasibility and small scale pilot efficacy of WC Services to increase CRC screening. We propose the following specific aims:

Specific Aim 1: Test the feasibility of WC Services to achieve CRC screening for non-adherent Medicaid clients. **Milestone 1a:** Achieve colonoscopy by a minimum of 60 out of 200 ($\geq 30\%$) patients contacted. **Milestone 1b:** Achieve CRC stool screening for 70 of the 140 colonoscopy non-adherent clients. **Milestone 1c:** WC Services will be revised to produce a new prototype to test in a Phase II based on findings.

Specific Aim 2: Develop an algorithm for predicting CRC screening outcomes following intervention services. **Milestone 2a.** Develop models based on existing R01 data to predict intent and CRC screening behaviors. **Milestone 2b.** Revise this R01 model incorporating new measures collected prospectively with 80% of clients contacted (n=160) to identify variations for likelihood of stool test v. colonoscopy completion.

Research Questions: **a)** Will Medicaid clientele, health insurers and physicians find WC Services usable and valuable for CRC screening? **b)** Will clients accept services and obtain colonoscopy or stool tests? **c)** Will current and/or new measures show predictive potential within Medicaid clientele for colonoscopy and/or stool tests? **d)** Will WC Services be able to increase screening enough to demonstrate potential for improving quality metrics for health insurance companies and primary care practices? Answering these research questions and achieving these aims (**Milestone 3:** Phase I Report), position us for a larger randomized controlled evaluation in Phase II while addressing important CRC screening disparities for the community and health care system.

5 METHODOLOGY

[figure not shown]
Overview. This Phase I small pilot efficacy and feasibility application is built upon the combined passion, persistence, science, expertise and experience from the following: a) Research on navigation for CRC screening (R01 CA 120658, [name], see Bio);²⁵ b) Years of community-based studies ([name], [name], [name], see Bios)^{10,16,26} resulting in the National Witness Project® (NWP) not-for-profit; c) Ability of the NWP to garner contracts for services from health insurance companies and health care providers (see Facilities and Resources); d) Results from our R01 (CA171935, MPIs: [name], [name], [name], see Bios);^{19,20,23} and e) Training through the NCI SPRINT Supplement ([name], [name], see Bios).²⁷ Based on this foundation, we now

are in a position to determine if we can combine this experience, data and expertise into a deliverable product (*WC Services*) that provides acceptable and appropriate services to non-adherent Medicaid clients resulting in effective CRC screening rates to meet the various requirements of health insurers (i.e., YourCare), primary care practices (Mercy Comprehensive Care Center- MCCC) and gastrointestinal endoscopy providers.

Product Concept. The proposed framework for services based on previous research^{19,28} is displayed in Figure 1. Encrypted lists of eligible clientele will be given to racially-concordant, call-center staff, including experienced navigators, according to established procedures by NWP. Scripts, based on [name]'s CRC screening protocol, will be used by navigators and call-center staff, including messaging and information that promotes positive affective associations with colonoscopy. From initial assessments and client responses, navigators will determine next steps following cues and flow chart experience (see Figure 1).

Based on assessments in real time, navigators will offer to send appropriate materials, messages and videos to clientele electronically and or by mail as requested to assist with clients' decision-making if they are not prepared for either colonoscopy or stool tests, and will be followed up by phone within two weeks. For clients

Figure 1. Framework for WC Services

Study Team: [name] (RPCI subcontract) and [name] will manage the science and *WC Services* activities, respectfully, as MPIs. The *WC Services* to Medicaid clients will be conducted by experienced team members contracted from the NWP (see Budget Justification). The pilot efficacy study benefits from the expertise of assembled colleagues Drs. [name] (Statistician), [name] (Consultant) and [name] (Consultant). The entire process and especially the feasibility assessments will be reviewed under the guidance of a five-member advisory board designed to offer expertise and counsel regarding 1) Technology transfer and potential commercialization issues (RPCI, [name]); 2) Needs and concerns of the health insurance industry (YourCare, [name]); 3) Needs and concerns of primary care clinical practices (MCCC, [name]/[name]); and 4) Science and clinical issues of colonoscopy and CRC screening (RPCI, [name]).

Aim 1: Test the feasibility of WC Services to achieve CRC screening for non-adherent

[figure not shown]
Medicaid clients. Based on previous experience and research (see Bios, Facilities), we hypothesize that we will be able to combine multi-level services to effectively assist $\geq 65\%$ of Medicaid clients from health insurer and clinical partners to obtain CRC screening in a 6-month trial during this Phase I. Achieving the milestones and benchmarks in Aim 1 will provide proof that we can improve screening metrics and meet the needs for our potential customers.

Partners, Recruitment and Participants. Witness CARES, LLC has established relationships with Mercy Comprehensive Care Center (MCCC), a local primary care practice serving a high proportion of Medicaid patients, and YourCare Health Plan, a Medicaid Managed health insurance company serving Buffalo, NY (see Facilities and Resources) to conduct this Phase I study (see Letters), and we will rely upon our Scientific Advisory Board (see Letters) to guide the conduct of the study, assuring that we are meeting the needs of customers, providing optimal services for clients/patients and truly achieving our feasibility measures in this study to effectively move forward into Phase II.

WC Services Flow Chart. To finalize details of the decision flow chart for contacting and providing services for CRC screening, [name] and [name] will work with the NWP navigators and call center staff to modify activity flow charts from current mammography screening, adding all details for CRC screening actions. We will also notify physicians including gastroenterologists and private and hospital colonoscopy facilities serving MCCC and YourCare patients that we are piloting new services for patients in the area, explain the services and obtain preferred colonoscopy prep instructions. MCCC and YourCare will assist with this process.

Pilot Study. Study participants will originate from MCCC and YourCare “gaps in care” lists of Medicaid/Medicare patients who are ages 50-75, have not had a stool test within 11 months, colonoscopy within 9 years and live in the Buffalo/Niagara Falls area. YourCare currently has a CRC gaps in care list of approximately 2500 clients and MCCC has 1599 patients for this study. From the NWP experience with insurers, we expect up to 48% of clients to be excluded (e.g., incorrect phone numbers, no longer insured, already screened). Therefore, we anticipate having a working list of at least 1,968 clients from which to contact over the approximately 26-week enrollment period (see Timeline Table 2). Based on prior experience with mammography screening for gaps in care clients, we know we can successfully contact \geq eight new clients per week (within the STTR budget) for a potential sample size of N=200 from the two sources (MCCC ~100 clients; YourCare~100 clients), which is expected to provide 80% power (at $\alpha=0.05$) (see Analysis of Aim 2 below). (Also See Figure 2. Study Schema).

Figure 2. Study Schema

Aim 2: Develop an algorithm for predicting CRC screening outcomes from intervention services.
We hypothesize that we will be able to identify a set of predictive measures, applicable for Medicaid clients and feasibly implementable, that will allow us to effectively predict which clients would be most likely to “convert” from not intending to screen to intending to screen following the receipt of WC Services and which

clients would be most likely to translate that intention to screen into actual engagement in specific screening behavior.

Data Sources and Participants: Specific Aim 2 will rely on a two pronged approach. First, we will leverage a rich, existing data resource collected as part of our recently completed community trial R01 of the WitnessCARES intervention for CRC screening (See Measures Table in Human Subjects). The data available from this study includes pre-intervention measures on a variety of psychosocial determinants of screening behavior, relevant demographic characteristics, intentions to screen both before and after the intervention, and, for a subset of participants, a 6 month follow-up report of actual screening behavior. The dataset contains 516 individuals who were: over age 50, self-identified as Black/African American, and either never screened or currently screening noncompliant. In addition to this secondary data analysis, we will collect and analyze new measures as a part of the methods described in Aim 1.

Proposed Secondary Data Analysis (Milestone 2a). The dataset from the WitnessCARES intervention study will provide us the ability to develop an initial iteration of a predictive tool to effectively identify two types of potential clients: a) individuals who, if they receive the intervention, are most likely to change from not intending to screen for CRC to intending to screen for CRC; b) individuals who intend to screen following the intervention but do not successfully convert that intention to actual engagement in screening behavior. To do so, we will use the individual items in the psychosocial and demographic measures collected pre-intervention to identify a subset of items that can successfully distinguish the types of potential clients described above. The analysis will proceed in 3 phases: variable reduction, screening intent model, and screening engagement model. *Variable Reduction:* Standard variable reduction techniques (such as principle components, missing values ratios, low variance filter, etc.) will be used to combine or exclude individual items (or sub-scales) for the candidate list of variables for model development. *Screening Intent Model:* Model development will proceed in two steps and will be based on available subjects. First, using a multivariable logistic regression model, main effects will be selected using a bootstrap backwards selection method (BBSM; alpha exit = 0.01). Second, potential two-way interactions between the selected main effects will

be identified using the BBSM (alpha exit = 0.001). The final model estimates for predicting screening engagement will be obtained using standard bootstrap methods. *Screening Engagement Model*: The model development will proceed as described for the screening intent model, except only subjects intending to be screened will be utilized. *Model Performance*: The screening intent and engagement models will produce predicted probabilities of intent and engagement based on subject characteristics. These probabilities are relatively subjective, so the Youden's index criterion will be used to identify a cut-off for both models that identifies which clients should be identified as "intending to screen" and "screening engaged". Model performance will be summarized using the receiver operating characteristic (ROC) curve and corresponding area under the ROC curve (AUC), and the sensitivity and specificity corresponding to the Youden's index cut-offs. *Alternative Approaches*: Classification and Regression Tree (CART) or other machine learning methods may be employed for the development of a classification model. In the presence of multiple models, models will be ranked by the specified performance measures.

Proposed Data Collection (Milestone 2b). For this secondary data analysis, as a part of the Aim 1 methods described above, navigators will invite all clients contacted to complete assessment items via telephone. Based on prior research and navigation experience, we know that clients are willing to complete health assessments and surveys of up to ~130 questions by phone if incentivized. This telephone assessment includes 118 self-report questions all of which have been used by the current team members with African American and Medicaid clients. However, we have never combined all of these items, and expect this to increase our capacity to identify impactful predictors. Based on prior experience, we are adding a Patient Activation Measure (PAM),²⁹⁻³² Process of Change (POC)^{33,34} for CRC screening and a 3-item unpublished, Navigator Subjective Assessment/Predictor (NSAP) by the navigator at the completion of the other questions (based on recent experiences by [name] and [name]). A similar data analysis strategy will be applied here. The 118 items will be used to predict differentiation of screeners from non-screeners as well as, among screeners, those who chose FIT versus colonoscopy (COL). Together, these are expected to significantly increase our predictive capacity for colonoscopy outcomes. We anticipate (Milestone 2b) being able to complete the survey with at least 160 clients during this Phase I.

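### The R01 engagement model's accuracy is planned only given intent, so no planned measure shows how well the tool finds, in advance, clients who will intend to screen but will not be screened

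*Combined protocol and SAP*

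**What the plan says.** All references are to the combined protocol and SAP.

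- **Purpose of the R01 tool** (Section 5, Aim 2, Milestone 2a). The R01 data are to be used to "develop an initial iteration of a predictive tool to effectively identify two types of potential clients". The second type, called type (b) here, is "individuals who intend to screen following the intervention but do not successfully convert that intention to actual engagement in screening behavior".
- **Predictors** (same paragraph). "we will use the individual items in the psychosocial and demographic measures collected pre-intervention", in order to "identify a subset of items that can successfully distinguish the types of potential clients described above".
- **Engagement model** (Screening Engagement Model). It is developed like the intent model, except that "only subjects intending to be screened will be utilized".
- **Performance** (Model Performance). Each model yields its own probability, and "the Youden's index criterion will be used to identify a cut-off for both models". ROC curve, AUC, sensitivity and specificity follow. The sample used for scoring is not named; the development sample is the natural reading.
- **Data.** The R01 set has 516 people, with intent recorded before and after the intervention. A 6-month report of screening exists for a subset whose size is not given.

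No section combines the two probabilities, and none plans an accuracy measure for type (b) over all R01 subjects.

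**The concern.** Type (b) has two parts: the person will form an intention, and will then not be screened. Before the intervention neither part is known. A tool that flags type (b) must therefore separate these people from two other groups: intenders who do get screened, and people who never come to intend. The engagement model is trained on the first contrast only, and would be scored on it alone if the development sample is used. Within known intenders, the second contrast does not arise.

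Milestone 2a could thus report a respectable engagement AUC while the promised task, recognising type (b) in advance, goes unmeasured. The R01 model is also the one that Milestone 2b updates and that leads to the Phase II prototype, so the gap would be carried forward.

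**Working it through.** **1. The plan's own figure.** The only accuracy-related figure for an engagement model is in Section 8, Aim 2: with n=160, a 95% confidence interval width of 0.14 at AUC 0.8 (0.10 at AUC 0.9). Using the Hanley-McNeil standard error, width = 2 x 1.96 x SE. With an assumed 80/80 split of screened and unscreened, the widths are 0.138 and 0.099, so the figures reproduce. They concern the precision of the updated model and do not bear on this point.

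**2. The target probability.** For pre-intervention items x, by definition:

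- P(type (b) | x) = P(intent | x) x [1 - P(engaged | intent, x)]
- P(screened | x) = P(intent | x) x P(engaged | intent, x) + [1 - P(intent | x)] x P(screened | no intent, x)

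The plan estimates P(intent | x) and P(engaged | intent, x) and scores each alone.

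**3. Who the comparators are.** Assume 60% intend and 50% of intenders are screened. Type (b) is then 0.60 x 0.50 = 30% of clients. The other 70% are 30% screened intenders and 40% non-intenders. So 40/70 = 57% of the comparators for type (b) come from a group that the engagement model never sees.

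**4. Size.** The documents give no intent rate, engagement rate or predictor strength, so all inputs here are assumptions. Simulation: 400,000 clients per scenario; standard normal intent and engagement scores with correlation rho; logistic models with the same slope for both; rates as in step 3; true probabilities used as scores, so no overfitting is included. AUCs at slope 0.95 / 1.25:

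| rho | Engagement score, intenders only | Engagement score, type (b), all clients | P(intent) x (1 - P(engaged given intent)), type (b), all clients |
|---|---|---|---|
| -0.5 | 0.73 / 0.77 | 0.72 / 0.77 | 0.75 / 0.80 |
| 0 | 0.73 / 0.78 | 0.66 / 0.70 | 0.71 / 0.76 |
| 0.3 | 0.73 / 0.78 | 0.62 / 0.65 | 0.69 / 0.73 |
| 0.6 | 0.73 / 0.77 | 0.58 / 0.59 | 0.66 / 0.70 |
| 0.9 | 0.72 / 0.76 | 0.53 / 0.53 | 0.61 / 0.65 |

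**5. Why it falls.** The all-client AUC is the weighted mean of two contrasts: 30/70 x (AUC against screened intenders) + 40/70 x (AUC against non-intenders). At rho=0.9 and slope 0.95, 0.530 = 0.429 x 0.720 + 0.571 x A, so A = 0.39. When the same traits drive intent and engagement, a low engagement score mostly marks people who will not intend at all. It then ranks them as likelier type (b) than the true type (b) clients.

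**6. The outcome of being screened.** With slope 0.95 and no non-intender screened, the intender-only AUC against the AUC of P(intent) x P(engaged | intent) in all clients is 0.73 v. 0.71 (rho=0), 0.73 v. 0.74 (0.3), 0.73 v. 0.75 (0.6) and 0.72 v. 0.77 (0.9). If 10% of non-intenders are screened, the all-client value is 0.70, 0.72 and 0.73 at rho 0.3, 0.6 and 0.9. The sign is not determined.

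**The case against.** **The conditional model answers a question the plan asks.** The Aim 2 hypothesis concerns which "clients would be most likely to translate that intention to screen into actual engagement in specific screening behavior", and type (b) is itself worded in terms of people who intend. Two stages, with engagement modelled given intent, are a deliberate and sound design. This stands, and it is why both conditional models should stay. It does not cover recognising type (b) from pre-intervention items, because intent is then part of what must be predicted.

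**Navigators may know intent when they use the score.** Section 9 (steps 2 to 4) has the navigator assess the client and treat those planning to be screened separately from the reluctant. Table 1 includes intention items. A reader might infer that nobody could ever obtain the conditional accuracies; this workflow shows otherwise. But it does not say when the R01 engagement score is applied, and it provides no accuracy measure for use before intent is known.

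**A general overstatement does not follow.** A reader might infer that the reported accuracy flatters the tool throughout. Step 6 shows that for being screened the difference can go either way. Even for type (b), the product score at rho=-0.5 slightly exceeds the intender-only AUC.

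**Nor do multiplied misses.** Applying both Youden cut-offs in series would, at rho=0 and slope 0.95, find about 44% of those later screened, against 65-68% for each model alone. No section prescribes series use, and in that scenario specificity rises from about 66% to about 81%. The loss cannot be charged to the plan.

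**Milestone 2a is a first iteration, and Phase I data follow.** Section 5 (Milestone 2b) plans a contrast of screeners with non-screeners, with no intent restriction in that sentence. That is a different outcome in different data and does not evaluate type (b) in the R01 set. Section 8 also labels the 160 as intending to screen, whereas Section 4 derives 160 as 80% of all clients contacted, so the population remains unclear there too.

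**Conclusion.** The point holds for type (b). The planned AUC, sensitivity and specificity of the engagement model apply given post-intervention intent. They do not tell the reader how well the tool finds future intenders who will not be screened when intent is unknown.

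Under the stated assumptions, the engagement score falls from AUC 0.72-0.78 among intenders to 0.53-0.77 for type (b) among all clients. The loss is negligible at rho=-0.5 and largest at rho=0.9. The product score reaches 0.61-0.80 and beats the engagement score at every correlation. The size depends on intent and engagement rates, slopes and correlation, none of which the documents give; the R01 data would show which case applies.

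This is a worthwhile, inexpensive improvement to a feasibility-stage analysis. It does not invalidate the two-stage design.

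**What to change.** 1. Keep the intent and engagement models and their separate AUCs. Label the engagement results as applying only once intent is known, and state when in the workflow the score is meant to be used.
2. For every R01 subject with a 6-month report, whatever the post-intervention intent, compute P(intent) x (1 - P(engaged | intent)). Score it against observed type (b) status, with its own Youden cut-off, AUC, sensitivity and specificity.
3. For predicting screening before intent is known, score P(intent) x P(engaged | intent) against observed screening in the same subjects. State that this omits screening among non-intenders, and add the last term of the formula in step 2 of the working if any such screening is observed.
4. Both products need P(intent) to be the probability of post-intervention intent for every subject scored, including those who already intended beforehand. The SAP should define the intent model's outcome accordingly.

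The cost is a paragraph of SAP text and a few lines of code on data already held. The reported type (b) accuracy may be less favourable than the conditional AUC. It can be computed only in the followed-up subset, so the size of that subset should be reported with it.
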